#### I. Purpose, Background and Rationale

#### A. Aim and Hypotheses

- 1. Sensory dysfunction as a result of peripheral nerve damage is a significant problem that leads to reduced quality of life for patients. The prevalence of sensory dysfunction in peripheral neuropathy associates with epidemic increases in prediabetes and diabetes, but also is relevant to chemotherapy treatments and genetic disorders. Clinical approaches to treat peripheral neuropathy and to stimulate axon growth in settings of peripheral axon loss are limited. Although new drugs will hopefully be forthcoming, the most promising approaches likely involve behavioral and lifestyle interventions. Mitochondrial dysfunction is emerging as a key cellular contribution to peripheral axon health and peripheral neuropathy. Mitochondrial deficiencies contribute to neuropathy and include impaired mitochondrial problems with trafficking, mitophagy, fission, and biogenesis. All of these are thought to lead to a bioenergetic crisis, ending in distal axonal degeneration, sensory dysfunction and pain. Heat shock proteins play a critically important role in cellular homeostasis and increasing heat shock protein functions within cells leads to a range of positive improvements, particularly in mitochondria. In addition, new evidence suggests that increasing heat shock protein responses in peripheral nerves has powerful, positive impacts on sensory function and neuropathy.
- 2. Our interdisciplinary team will investigate the role of mitochondrial dysfunction in peripheral neuropathy and translate these approaches to improve treatment for patients with peripheral neuropathy. We hypothesize that novel heat treatment interventions that improve mitochondrial function will improve metabolic symptoms and peripheral nerve mitochondria, leading to improvements in sensory function, via heat shock protein induction. We will employ immersion heat treatment to elevate heat shock protein responses that induce positive changes in peripheral nerve mitochondria. One aspect is to confirm the efficacy, safety, and potential for heat treatment to improve sensory dysfunction in human patients with prediabetes. The goal of this proposal is 1) to test the breadth of heat treatment on various forms of neuropathy, 2) identify mechanisms in which heat treatment improves mitochondrial function, and 3) test the efficacy, safety, and potential function, and 3) test the efficacy, safety, and potential for heat treatment in muman patients with prediabetes.

#### **B. Background and Significance**

 Study Significance: Diabetic neuropathy (DN) is a common prediabetic and diabetic complication and is a leading cause for disability due to foot ulceration and amputation, gait disturbance, and fall-related injury. Sensory dysfunction in peripheral neuropathy (PN) is also is relevant to chemotherapy treatments and genetic disorders. Compared to

KUMC – HRPP- 03/12/2015

diabetic patients without neuropathy, patients with DN experience a twofold increase in health-care costs, and those with severe painful peripheral neuropathy experience a fourfold increase. In addition, 25% of patients with prediabetes also develop PN. Currently, there are no treatments for diabetic and prediabetic PN other than pain control. This problem must be addressed as our global population with diabetes increases in epidemic proportions. The scientific premise of our application is based on the evidence from both preclinical and clinical studies.

- 2. The reliance of peripheral neurons on proper mitochondrial support for their maintenance has emerged as a key mechanism underlying neuropathy. In diabetic neuropathy, a number of recent studies have reported deficient mitochondrial support. Thus, approaches to improve mitochondrial function and stimulate new mitochondrial biogenesis are logical directions to treat peripheral neuropathy. Heat shock is one of the best-known interventions that lead to changes in gene expression known to improve mitochondrial function. New evidence is emerging that heat treatment leads to a significant enhancement of heat shock protein effects in a number of organ systems. A key step in leading to this proposal was the successful implementation of a hot tub in the CTSU that now allows us to heat treat patients and test the hypothesis that heat treatment stimulates heat-shock protein mediated mitochondrial improvements related to glucose control and nerve function.
- 3. Literature Review: **Peripheral neuropathy is strongly associated with metabolic syndrome and diabetes**. Current strategies to prevent diabetic PN focus on glucose control and lifestyle modifications. Improved glucose control dramatically reduces the incidence of PN in type 1 and type 2 diabetes. Current clinical recommendations focus on optimizing glucose control to prevent or delay the development of diabetic PN. New approaches that contribute to better glucose control are needed.

#### Peripheral neuropathy is associated with mitochondrial dysfunction.

Mitochondrial dysfunction is a key cellular contributor to peripheral axon health. Mitochondrial deficiencies contribute to neuropathy and include impaired mitochondrial problems with trafficking, mitophagy, fission, and biogenesis. Together, this leads to a bioenergetic crisis, ending in distal axonal degeneration and sensory dysfunction. Heat shock proteins play a critically important role in cellular homeostasis and increasing heat shock proteins improves neuronal health.

**Heat treatment reduces abnormal metabolic changes in diabetes**. Several studies have reported metabolic benefits in type 2 diabetes patients with heat therapy. In these studies, 3 weeks of heat treatment reduced plasma glucose and HbA1c levels. Additional studies using heat therapy in obese patients report improvements in quality of life and reduced weight and fat. Thus, an additional benefit of heat treatment may be to reduce detrimental metabolic changes that contribute to PN.

**Heat treatment stimulates heat shock protein levels and improves mitochondrial function in patients**. Ongoing studies are assessing the ability of heat therapy to impact mitochondria in human subjects (ages 28-45, n=5). A skeletal muscle biopsy was performed at the KU Clinical Research Center (CRC). One week later, subjects underwent 60 min of heat exposure (hot tub) located in the CRC. Subjects then returned 24 h after the heat therapy for a second muscle biopsy. Muscle samples were analyzed for heat shock protein levels and respiratory measures. These studies reveal that skeletal muscle respiratory capacity increases following acute heat therapy. Moreover, these studies suggest that heat treatment increases heat shock proteins in muscle that positively

correlate with increased mitochondrial respiration. These findings are consistent with our preclinical studies of heat therapy in rodents.

# C. Rationale

- Literature from our own studies and others reveal that heat treatment leads to beneficial heat-shock-mediated improvements in glucose control and mitochondrial function. Studies now reveal that deficient energy support from mitochondria in peripheral nerves is a significant contributor to impaired nerve function and neuropathy.
- 2. Success in this project will reveal a new intervention for patients suffering from nerve damage and sensory dysfunction. Currently, there are no treatments other than pain control for patients with peripheral neuropathy. Heat treatment likely can be combined with healthy lifestyle and exercise to benefit patients suffering from neuropathy. The project will also provide new information about how heat treatment may improve glucose control in humans with prediabetes or diabetes.
- 3. The information gained in this research study will be useful in developing fundamental knowledge about heat therapy and determining if heat therapy can be a novel treatment of peripheral neuropathy related to prediabetes patients.

# II. Research Plan and Design

- **A. Study Objectives:** To see if heat therapy can be used to improve metabolic symptoms and peripheral nerve mitochondria, leading to improvements in sensory function.
- **B. Study Type and Design:** This prospective, observational cohort pilot study will recruit 20 patients with prediabetes with or without peripheral neuropathy (painful and non-painful) to participate in a 4-week heat therapy intervention. After screening, informed consent, and enrollment into the study, subjects will undergo a pre-intervention evaluation that will assess metabolic biomarkers and heat shock protein levels (blood), peripheral neuropathy, and epidermal evaluation (skin biopsy). After the skin biopsy has the appropriate time to heal (approximately 7-14 days), the subjects will undergo 45-minute heat treatments in 40°C water, three times weekly, for 4 weeks. After completion of heat treatments, subjects will undergo a repeated post-intervention evaluation and skin biopsy. Statistical approaches will compare pre– and post-heat therapy measures.

## C. Sample size, statistical methods, and power calculation

- 1. Subjects will not be randomized as our study is a pilot intervention of subjects with prediabetes and neuropathy. Analyses of pre- treatment vs. post-treatment outcomes will be performed using ANOVA. The primary goal of this pilot study will be to provide necessary data for a power analysis to estimate the effect size for design of a larger future study.
- 2. N/A
- 3. 20 subjects will receive intervention. As this is a pilot study which will be used to inform future, larger studies, power calculations will not be needed. Statistical approaches will compare pre- and post-heat therapy measures.

## D. Subject Criteria (See Vulnerable Populations appendix, if applicable):

1. Inclusion criteria: Subjects will include both males and females, ages 45-75, that have suspected or diagnosed prediabetes with or without neuropathy (to be confirmed at pre-intervention evaluation).

- 2. Exclusion criteria: (1) skin conditions, circulatory insufficiency, or open wounds in the leg that would interfere with healing from a biopsy;
  - (2) stroke or other significant nervous system pathology;
  - (3) lidocaine allergy;
  - (4) anticipated difficulty with blood clotting due to disorder or use of a blood thinner such as Coumadin, Xarelto, or Eliquis;
  - (5) use of any medication used to treat abnormal blood glucose such as Metformin;
  - (6) body weight > 350 lbs.;
  - (7) history of anemia or vitamin b12 deficiency;
  - (8) clinical anemia (hematocrit <32 for women, <36 for men);
  - (9) abnormal SPEP result;
  - (10) history of cancer or chemotherapy treatment;
  - (11) current or recent use (within the last 6 months) of artificial fingernails / nail enhancements that would interfere with quantitative sensory testing;

(12) no special classes of subjects such as fetuses, neonates, pregnant women, prisoners, institutionalized individuals, non-English speaking individuals, or other who may be considered vulnerable populations will be included in this study.

- 3. Withdrawal/Termination criteria: Prediabetes will be determined using the American Diabetes Association (ADA) Diabetes Management Guidelines. The subject will meet the criteria for a diagnosis of pre-diabetes if the subject has one or more positive test(s) for either A1c (5.7-6.4%), fasting glucose (100-125 mg/dl), or 2-hr oral glucose tolerance test (140-199 mg/dl). If at pre-intervention evaluation, the subject does not meet the criteria for prediabetes (lower than the above-mentioned range), meets the ADA criteria for diabetes (higher than the above-mentioned range), the subject will be considered a screen fail and will not progress to skin biopsy or intervention.
- 4. Subject may participate in other observational studies but cannot participate in other studies in which they receive an intervention.

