Visit 2 (pre-intervention evaluation): Once inclusion and exclusion criteria are confirmed by laboratory results, the presence and type of neuropathy will be confirmed with a clinical examination and nerve function testing (Drs. [name] or [name], approx. 1.5 hours).

Neuropathy and Pain Assessment: medical evaluation by Drs. [name] and [name], Utah Early Neuropathy Scale (UENS), Quantitative Sensory Testing (QST). Questionnaires: Brief Pain Inventory (BPI), PROMIS Physical Function short form. Skin Biopsy: Patients will undergo a punch skin biopsy from the proximal thigh. Total dermal and epidermal innervation will be quantified from skin biopsies. The punch skin biopsy will be performed using a 3 mm disposable circular punch (Miltex, York, PA) after injection of 2% lidocaine under a sterile technique. No suture will be used. The skin will be placed in freshly prepared Zamboni's fixative for one hour. The tissue will be sectioned at 50 µm and processed for immunohistochemistry using rabbit anti-PGP9.5 primary antibody (1:3000; Chemicon, Temecula, CA). Sections will be coded in order to carry out the analysis in a blinded fashion and quantified. The biopsy will be used for quantification of GLO1 enzymatic activity.

Visits 3-14 (heat therapy intervention x 12 treatments): After the skin biopsy has appropriate time to heal (approximately 7-14 days), the subjects will undergo 30-minute heat treatments in 40°C water, three times weekly, for 4 weeks (approx. 1 hour each).

[figure not shown]
Subjects will be immersed up to the shoulder in a 40°C hot tub until rectal temperature  $(T_{re})$  increases by 1°C (~20 minutes). Subjects will then remain in the water bath submerged to waist level to maintain Tre between 38.5 and 39.0°C for another 30 minutes (approx. total time submerged ~50 minutes). Following hot water immersion, subjects will be monitored for another 10 min, or until Tre falls below 38.5°C. Core temperature will be monitored using either 1) a rectal probe with sterile disposable sheaths or 2) a sterile disposable rectal thermistor probe (401 A/C, Advanced Industrial Systems, Inc., Harrods Creek, KY) to be inserted  $\sim 1$  inch past the anal sphincter

(inserted by participant). Heart rate and blood pressure will be monitored throughout the treatment. Subjects will be continually monitored and removed from the hot bath if  $T_{re}$  exceeds 39.5°C.

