The 3mm skin biopsy procedure is not painful. However, when the Lidocaine is injected, there may be a brief pinprick pain followed by a few seconds of burning form the anesthesia. A small percentage of patients can have an allergic reaction to the Lidocaine. If an allergic reaction to the Lidocaine occurs, it will be treated immediately with medicines in the clinic. Following the biopsy there will probably be some soreness. There is a risk that the biopsy site will bleed or become infected. The risk for infection is low at the biopsy site. The biopsy will leave a small scar that will fade in intensity over time. There are some risks associated with heat exposure, including: fatigue, light-headedness, muscle cramps, dehydration, and neurological detriments (i.e. heat stroke). However, these symptoms do not typically occur until core temperature rises above 40°C. Core temperature (rectal thermistor) will be continuously monitored and recorded. Subjects will be removed from the hot bath immediately if either core temperature reaches 39.5°C or the subjects experience any symptoms of heat-related illness. All symptoms subside upon lowering core temperature. Ice packs will be on hand if rapid cooling is necessary (see Rapid Cooling SOP). Heart rate will also be continuously monitored and recorded throughout heating. If HR increases > 60 beats/min above resting or increases > 20beat/min with a 5 min time period, subjects will be moved to a seated position if they were previously fully submerged or removed from the hot tub if they were already sitting up. Additionally, heat exposure may have detrimental effect on a developing fetus in females. Thus, subjects who are pregnant or trying to conceive will be excluded from the study. This will be confirmed with a pregnancy test.

- 2. Psychological risk: Some questions related to medical history, weight, or pain status may result in feelings of discomfort or embarrassment. Participants may decline to answer any questions.
- 3. Social risk: N/A
- 4. Economic risk: N/A

- 5. Potential benefit of participating in the study

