  - a. Potential benefits for individuals including learning new information based on laboratory testing and medical examination, at no cost to the subject. This information may be of use to the participant and their physician by providing updated information on important parameters of prediabetes and/or neuropathy. Subjects will have the opportunity to receive heat therapy, which may offer multiple health benefits related to the cardiovascular system and metabolic health. Physiological benefits to the cardiovascular system in healthy subjects has been documented and those studies were performed by [name], from the University of Oregon. In addition, quality of life improvements have commonly been reported by patients undergoing chronic heat exposure (e.g. hot tub, sauna, etc.).
  - b. The information gained in this research study will be useful in developing novel treatments of peripheral neuropathy in the future related to prediabetes patients.
  - c. The proposed research will be helpful to develop fundamental knowledge about treatment approaches that will help reduce the burdens of disease and disability. This knowledge should offset the very minor risk to participation by individual subjects, given the protections that are in place and the low likelihood of a serious adverse event in this study.

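### Apart from pregnancy or trying to conceive, no eligibility rule in the text covers fitness for repeated heating to 38.5-39.0°C in subjects aged 45-75

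*Combined protocol and SAP*

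**What the plan says.** **Exposure (II.D.1; II.E, Visits 3-14).** Men and women aged 45-75 sit in 40°C water up to the shoulder until rectal temperature has risen by 1°C, which takes about 20 minutes. They then stay in to the waist for 30 minutes at 38.5-39.0°C. There are 12 sessions.

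**Exclusions (II.D.2).** There are 12 items. The only one with circulatory wording is item (1): "skin conditions, circulatory insufficiency, or open wounds in the leg that would interfere with healing from a biopsy".

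**Heat-based exclusion (II.F.1).** After noting possible harm to a fetus, the plan says: "Thus, subjects who are pregnant or trying to conceive will be excluded from the study".

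**Assessment before heating (II.E).** A phone screen goes through the eligibility criteria. Visit 1 records medical history, medications, heart rate and blood pressure. At Visit 2, "the presence and type of neuropathy will be confirmed with a clinical examination and nerve function testing".

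**In-session rules (II.F.1).** "Subjects will be removed from the hot bath immediately if either core temperature reaches 39.5°C or the subjects experience any symptoms of heat-related illness". There is also a heart-rate rule, which begins "If HR increases > 60 beats/min above resting or increases > 20beat/min with a 5 min time period"; its first step is that "subjects will be moved to a seated position if they were previously fully submerged", and a subject already sitting up is taken out. On the listed heat symptoms the section says: "However, these symptoms do not typically occur until core temperature rises above 40°C".

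**The concern.** The plan treats heat as a circulatory load. It sets heart-rate limits, monitors blood pressure in every session, and lists light-headedness and dehydration among the heat risks. It also accepts that fitness for heat can decide eligibility, since it excludes people who are pregnant or trying to conceive for that reason. The eligibility text takes this no further. As written, a 60-year-old with unstable heart disease or recurrent fainting who met the other criteria could go on to the first immersion without breaking any rule shown.

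Subject safety is the main stake. Section I.A also names safety among the aims, although II.C.1 gives the pilot's primary goal as data for an effect size. Section II.L discontinues any subject who has a serious adverse event, so each such event would remove 1/20 = 5% of a 20-subject pre-post sample.

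**Working it through.** The plan gives no figure to reproduce here. The check sets the eligibility text against the exposure.

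1. **Session count.** 3 per week × 4 weeks = 12, and Visits 3 to 14 are 14 − 3 + 1 = 12. The two agree.

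2. **The 12 exclusions against four conditions.** Items naming heart disease: 0 of 12. Blood pressure: 0 of 12. Syncope: 0 of 12. Previous heat illness: 0 of 12. No item gives the investigator discretion to exclude someone as unfit for heat. Where the list states a purpose, it is biopsy healing (item 1), clotting (item 4) or sensory testing (item 11).

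3. **Incidental coverage.** Stroke, blood thinners, anemia, weight above 350 lbs and a cancer or chemotherapy history will remove some people at higher risk. None of these is framed as a heat criterion, and none covers the four conditions as a group.

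4. **Item (1).** It can be read as excluding circulatory insufficiency outright, or only where a leg biopsy would heal poorly. Neither reading supplies a blood-pressure, syncope or heat-illness rule, or names heart disease.

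5. **Heat-based exclusions elsewhere.** The only one found is in II.F.1. Pregnancy also appears in II.D.2 item (12), without a heat reason. Trying to conceive appears only in II.F.1.

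6. **What happens before heating.**
   - Phone screen: its stated job is to review the listed criteria. The form itself is not shown.
   - Visit 1: history, medications and laboratory tests serve to confirm the listed criteria. Heart rate and blood pressure are recorded with no limit.
   - Visit 2: a physician examination, whose stated purpose is neuropathy.

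   None of these carries a written rule on fitness for heat.

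7. **What happens once heating begins.**
   - Removal at 39.5°C or on symptoms of heat illness.
   - Two heart-rate limits.
   - Blood-pressure monitoring, with no action value stated.
   - Monitoring after immersion for 10 minutes or until rectal temperature is below 38.5°C.
   - Ice packs and a Rapid Cooling SOP.
   - A decision by the principal investigator, after each adverse event, on whether to continue (II.L).
   - Discontinuation after a serious adverse event (II.L).

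   All of these follow the first exposure.

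**The case against.** Four arguments run the other way.

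- **The deciding form may be unseen.** The phone screen is in an appendix and the screening questionnaire (III.B) is attached; neither is in the text reviewed. The trying-to-conceive rule in II.F.1 shows that an eligibility rule can sit outside II.D.2. This stands as a limit: the supportable claim is that no such rule is visible. It is weakened by the phone screen's stated job, which is to review the listed criteria.
- **The risk premise comes from outside the documents.** No section says that the named conditions make immersion more dangerous. The plan's own view is that heat symptoms are not typical below 40°C, and removal is set at 39.5°C. This also stands: the premise is clinical judgement.
- **The controls are strong and partly individual.** The investigator's decision after each adverse event can take a subject's history into account. That narrows the gap but cannot act before the first immersion.
- **Clinicians see every subject twice before heating and may exclude informally.** They may, but no written rule tells them to, so practice could differ between subjects or staff.

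**Conclusion.** The point holds in a limited form. In the text reviewed, fitness for heat affects eligibility only through pregnancy or trying to conceive, and the safeguards that would protect other people at risk start after heating does. A written rule should be added; confidence is medium. The conclusion assumes that the unseen forms add no such rule and that the named conditions do raise risk. Neither the number of affected candidates nor a harm rate can be estimated from the documents.

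Four stronger readings are not supported:

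- **That people with unstable heart disease will be heated, or that the trial is unsafe.** The text permits such enrolment; it does not show that it will happen.
- **That the heart-rate limits measure the gap.** They govern what is tolerated in the tub, not who enters it, and a new exclusion would leave them unchanged.
- **That the cited evidence leaves out people with heart disease.** Section II.F.5 says "Physiological benefits to the cardiovascular system in healthy subjects has been documented", and the team's own hot-tub data in I.B come from five people aged 28-45. But I.B also cites studies in type 2 diabetes and obesity without giving their cardiac eligibility, so what they cover cannot be known here.
- **That item (1) must extend to wounds anywhere on the immersed body.** Nothing in the plan establishes a problem there.

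**What to change.** Add one item to II.D.2: symptomatic or unstable heart disease, uncontrolled or low blood pressure, recurrent syncope, previous heat illness, or another condition that in the investigator's judgement makes repeated hot-water immersion unsafe.

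Apply it before the first session, using the history, medication review, heart rate and blood pressure already collected at Visit 1. Deciding at Visit 1 would also spare an unsuitable candidate the Visit 2 skin biopsy. If the phone screen already asks about these conditions, carry its rule into II.D.2 so that the eligibility list is complete.

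The cost is protocol wording, matching phone-screen wording and a line on the Visit 1 eligibility checklist, with no new procedure. The downside is a few more screen failures (the number cannot be estimated here) and results that apply to people with prediabetes who are fit for heat exposure.
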